10.7.1. Telehealth Visits

In the event that in-clinic study visits cannot be conducted, every effort should be made to follow up on the safety of study participants at scheduled visits per the [Schedule of Activities](#) or unscheduled visits. Telehealth visits may be used to continue to assess participant safety and collect data points. Telehealth includes the exchange of healthcare information and services via telecommunication technologies (eg, audio, video, video-conferencing software) remotely, allowing the participant and the investigator to communicate on aspects of clinical care, including medical advice, reminders, education, and safety monitoring. The following assessments must be performed during a telehealth visit:

- Review and record study intervention(s), including compliance and missed doses.
- Review and record any AEs and SAEs since the last contact. Refer [Section 8.3](#) and [Appendix 3](#).
- Review and record any new concomitant medications or changes in concomitant medications since the last contact.
- Review and record contraceptive method and results of pregnancy testing. Confirm that the participant is adhering to the contraception method(s) required in the protocol. Refer to [Appendix 4](#) and [Section 10.7.2.1](#) of this appendix regarding pregnancy tests.

Study participants must be reminded to promptly notify site staff about any change in their health status.

10.7.2. Alternative Facilities for Safety Assessments

10.7.2.1. Laboratory Testing

If a study participant is unable to visit the site for protocol-specified safety laboratory evaluations, testing may be conducted at a local laboratory if permitted by local regulations. The local laboratory may be a standalone institution or within a hospital. The following safety laboratory evaluations may be performed at a local laboratory:

- Hematology
- Chemistry

- Coagulation: PT/INR, PTT/aPTT
- Urinalysis

If a local laboratory is used, qualified study site personnel must order, receive, and review results. Site staff must collect the local laboratory reference ranges and certifications/accreditations for filing at the site. Laboratory test results are to be provided to the site staff as soon as possible. The local laboratory reports should be filed in the participant's source documents/medical records.

If a participant requiring pregnancy testing cannot visit a local laboratory for pregnancy testing, a home urine pregnancy testing kit with a sensitivity of at least 25 IU/mL may be used by the participant to perform the test at home, if compliant with local regulatory requirements. The pregnancy test outcome should be documented in the participant's source documents/medical records. Confirm that the participant is adhering to the contraception method(s) required in the protocol.

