4. STUDY DESIGN

4.1. Overall Design

Study design is as described in the B1371019 Protocol (Amendment 5, 12 April 2019) and Study B1371012 Protocol (Amendment 7, 14 June 2018). This is an open-label, continuation protocol for eligible NINT cohort participants enrolled in Study B1371019 or Study B1371012 eligible participants.

Following a planned interim analysis on 30 September 2020 for the INT cohort, Pfizer accepted the Committee's EDMC conclusion that glasdegib offered no survival benefit.

A maximum of 34 unblinded participants from Study B1371019 and 3 participants originating from Study B1371012 who continue to derive clinical benefit per the treating investigators will be allowed access to the study intervention per Amendment 6.

Amendment 6 is a continuation protocol for NINT cohort participants from Study B1371019 or Study B1371012. A maximum of 34 participants from Study B1371019 and 3 participants from Study B1371012 will continue to receive access to study intervention.

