5.3. Lifestyle Considerations

5.3.1. Contraception

Glasdegib has been associated with teratogenic risk and azacitidine has been shown to cause congenital malformations in animals. The investigator or his or her designee, in consultation with the participant, will confirm that the participant has selected an appropriate method of contraception for the individual participant and his or her partner(s) from the permitted list of contraception methods (see [Appendix 4 Section 10.4.4](#)) and will confirm that the participant has been instructed in its consistent and correct use. At time points indicated in the [SoA](#), the investigator or designee will inform the participant of the need to use highly effective contraception consistently and correctly and document the conversation and the participant's affirmation in the participant's chart (participants need to affirm their consistent and correct use of at least 1 of the selected methods of contraception). In addition, the investigator or designee will instruct the participant to call immediately if the selected contraception method is discontinued or if pregnancy is known or suspected in the participant or partner.

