6.1.3. Treatment Duration

Treatment with the study treatment should be continued until objective disease progression or relapse, death, unacceptable toxicity, or participant refusal, whichever occurs first.

If glasdegib is permanently discontinued for reasons other than objective disease progression, participant refusal, or consent withdrawal, single agent treatment with azacitidine may be continued if, in the Investigator's judgment, a clinical benefit has been observed and following discussion between the investigator and sponsor.

In cases of unacceptable toxicity or pregnancy, the participant must be withdrawn from study treatment.

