8.2.3. Pregnancy Testing

Pregnancy tests may be urine or serum tests, but must have a sensitivity of at least 25 mIU/mL. Pregnancy tests will be performed in WOCBP at the times listed in the [SoA](#). Following a negative pregnancy test result at screening, appropriate contraception must be commenced, and a second negative pregnancy test result will be required at the baseline visit prior the participant's receiving the study intervention/study treatment. Pregnancy tests will also be done whenever 1 menstrual cycle is missed during the active treatment period (or when potential pregnancy is otherwise suspected) and at the end of the study treatment. Pregnancy tests may also be repeated if requested by IRBs/ECs or if required by local regulations. If a urine test cannot be confirmed as negative (eg, an ambiguous result), a serum pregnancy test is required. In such cases, the participant must be excluded if the serum pregnancy result is positive.

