10.7. Appendix 7: Alternative Measures During Public Emergencies

The alternative study measures described in this section are to be followed during public emergencies, including the COVID-19 pandemic. This appendix applies for the duration of the COVID-19 pandemic globally and will become effective for other public emergencies only upon written notification from Pfizer.

Use of these alternative study measures are expected to cease upon the return of business as usual circumstances (including the lifting of any quarantines and travel bans/advisories).

Details for entering the data in the CRF are described in the CRF Completion Guidelines.

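### Protocol Section 10.7.2.1 sets the home pregnancy-test sensitivity at 25 IU/mL, 1000 times looser than the 25 mIU/mL in Section 8.2.3; almost certainly a dropped 'm'

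*Protocol*

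**What the plan says.** Protocol Section 8.2.3 gives the general rule: "Pregnancy tests may be urine or serum tests, but must have a sensitivity of at least 25 mIU/mL". It applies to urine and serum tests alike and does not set home tests apart.

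Appendix 7 covers public emergencies. Its Section 10.7.2.1 deals with a participant who cannot reach a local laboratory for pregnancy testing. In that case, subject to local regulations, "a home urine pregnancy testing kit with a sensitivity of at least 25 IU/mL may be used by the participant".

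The appendix was live text for this amendment: "This appendix applies for the duration of the COVID-19 pandemic globally". Section 8 directs sites to it for the pandemic period. For telehealth visits, Section 10.7.1 requires the contraceptive method and pregnancy test results to be reviewed. It points to Appendix 4 and to Section 10.7.2.1 "of this appendix regarding pregnancy tests". It does not cite Section 8.2.3, and Appendix 4 gives no test sensitivity.

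**The concern.** Two current sections give different minimum sensitivities for the same kind of test, with the same number and a unit that differs by a factor of 1000. Nothing in the protocol explains why a home kit should be held to a looser standard.

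The figure matters because of the drugs involved: "Glasdegib has been associated with teratogenic risk and azacitidine has been shown to cause congenital malformations in animals". A positive result also has a direct consequence: "In cases of unacceptable toxicity or pregnancy, the participant must be withdrawn from study treatment". The Schedule of Activities lists the pregnancy test and contraception check at screening, on Day 1 of each cycle and at end of treatment. Section 10.7.3 allows study intervention to be couriered to participants where local rules permit, so a woman could receive oral glasdegib at home with a home kit as her pregnancy test. If the printed figure were followed, a kit far too insensitive under Section 8.2.3 would be acceptable, and an early pregnancy could be missed while dosing continued.

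**Working it through.** **Inputs**

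- General minimum sensitivity, urine or serum (Section 8.2.3): 25 mIU/mL.
- Home urine kit minimum sensitivity (Section 10.7.2.1): 25 IU/mL.
- Size of the continuation population (Section 4.1): "A maximum of 34 unblinded participants from Study B1371019 and 3 participants originating from Study B1371012".

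**Unit conversion**

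1 IU = 1000 mIU, so 25 IU/mL × 1000 mIU/IU = 25,000 mIU/mL.

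**Ratio of the two limits**

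25,000 mIU/mL ÷ 25 mIU/mL = 1000.

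Read literally, any kit with a detection limit above 25 and up to 25,000 mIU/mL would pass Section 10.7.2.1 and fail Section 8.2.3. With the unit corrected, the ratio is 25 ÷ 25 = 1 and the two sections agree.

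**Number of people who could be affected**

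The upper bound on participants is 34 + 3 = 37. Those exposed to the wrong figure are the women of childbearing potential among them who cannot reach a local laboratory while Appendix 7 is in force and whose local rules allow home testing. The documents do not give that number, so the range is 0 to some part of 37.

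**Which figure is the error**

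The two sentences share the number and the form of the requirement, and only the prefix differs. Section 8.2.3 is the general, mandatory rule. Section 10.7.2.1 is a logistical allowance about where the test is done and does not claim to change its standard. A lost prefix in Section 10.7.2.1 is therefore by far the likeliest explanation, though it remains an inference.

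**The case against.** The strongest reply is that Section 8.2.3 already governs. It is mandatory and general, while Section 10.7.2.1 only permits a home kit and does not say that it replaces the earlier rule. A kit that detects 25 mIU/mL satisfies both sections, so a site that reads the whole protocol will choose correctly. The missing cross-reference in Section 10.7.1 does not switch Section 8.2.3 off. All of this is right, and it limits the harm. It does not make the printed figure correct, and a site working only from Appendix 7 would not come across the right one.

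The route to exposure is also narrow. All participants are on azacitidine with or without glasdegib. Azacitidine is given by injection or infusion around Days 1 to 7 of each cycle, and the routine on-treatment pregnancy test falls on Day 1. A woman being dosed would usually be at a treatment centre when the test is due. Home testing would mainly concern end-of-treatment, delayed-cycle or unscheduled tests. This point stands too.

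Other safeguards remain: highly effective contraception, contraception checks, a test after a missed menstrual cycle, and a serum test when a urine result is unclear. The last two are weaker if the wrong limit is applied. A plainly negative but false result would not trigger the serum test, and the missed-cycle test could be done with the same kit.

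The factor of 1000 measures the gap between two printed units and is not an observed effect. Nothing in the documents shows that so insensitive a kit exists or would be supplied.

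Finally, a single letter can be lost when a PDF is converted to text. The surrounding text is intact and Section 8.2.3 kept its prefix, so this is unlikely. A look at the source page settles it.

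**Conclusion.** The concern holds. The sensitivity limit in Section 10.7.2.1 is wrong as written: it is 1000 times the limit in Section 8.2.3, and no reason is given for a difference. It should be corrected because it is an operative safety threshold for drugs with teratogenic risk, in an appendix that applied throughout the COVID-19 pandemic.

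The practical effect is limited to a subset, possibly empty, of at most 37 participants, and no endpoint, analysis set or estimate depends on it. The conclusion assumes that 25 mIU/mL is the intended minimum everywhere and that the missing prefix is in the protocol itself.

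**What to change.** In Section 10.7.2.1, change the unit from IU/mL to mIU/mL. Alternatively, remove the figure and refer to Section 8.2.3, so that the requirement is stated only once. Send sites a short note of the correction.

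The cost is a one-letter protocol correction and the note. Data collection and analysis do not change, and the SAP needs no amendment.

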10.7.3. Study Intervention

If the safety of a trial participant is at risk because they cannot complete required evaluations or adhere to critical mitigation steps, then discontinuing that participant from study intervention must be considered.

Study intervention may be shipped by courier to study participants if permitted by local regulations and in accordance with storage and transportation requirements for the study intervention. Pfizer does not permit the shipment of study intervention by mail. The tracking record of shipments and the chain of custody of study intervention must be kept in the participant's source documents/medical records.

The following is recommended for the administration of study intervention for participants who have active [confirmed (positive by regulatory authority-approved test) or presumed (test pending/clinical suspicion)] SARS-CoV2 infection:

- For symptomatic participants with active SARS-CoV2 infection, study intervention should be delayed for at least 14 days from the start of symptoms. This delay is intended to allow the resolution of symptoms of SARS-CoV2 infection.
- Prior to restarting treatment, the participant should be afebrile for 72 hours, and SARS-CoV2-related symptoms should have recovered to \leq Grade 1 for a minimum of 72 hours. Notify the study team when treatment is restarted.
- Continue to consider potential drug-drug interactions as described in [Section 6.5](#) for any concomitant medication administered for treatment of SARS-CoV2 infection.

10.7.4. Adverse Events and Serious Adverse Events

If a participant has COVID-19 during the study, this should be reported as an AE or SAE and appropriate medical intervention provided. Study treatment should continue unless the

investigator/treating physician is concerned about the safety of the participant, in which case temporary or permanent discontinuation may be required.

It is recommended that the investigator discuss temporary or permanent discontinuation of study intervention with the study medical monitor.

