### **6.2.3.6. Dose Reductions and Interruptions due to Adverse Events**

A dose reduction due to an AE is defined as a non-zero dose where reason for adjustment on the dosing CRF is AE.

The number and percentage of patients with at least one dose reduction as well as a breakdown of dose reductions (1 / 2 /  $\geq 3$ ) and/or the dosage administered will be summarized by treatment and by treatment arm.

An interruption due to an AE is defined as a 0 mg dose administered where reason for adjustment on the dosing CRF is AE. The number and percentage of patients with dose interruptions will be summarized by treatment and by treatment arm. Percentages will be calculated based on the total number of patients in the safety analysis set.

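### Protocol Sections 10.7.3 and 10.7.4 give opposite dosing defaults for a participant with symptomatic COVID-19 about whom the investigator has no safety concern

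*Protocol*

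**What the plan says.** Both texts are current provisions of Protocol Appendix 7, not amendment history. The appendix is in force: "This appendix applies for the duration of the COVID-19 pandemic globally".

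Section 10.7.3 (Study Intervention) opens its guidance with "The following is recommended for the administration of study intervention for participants who have active" infection, and defines active as either confirmed or presumed. For symptomatic participants, "study intervention should be delayed for at least 14 days from the start of symptoms". It then sets restart conditions: "Prior to restarting treatment, the participant should be afebrile for 72 hours", and symptoms must have been at Grade 1 or lower for at least 72 hours.

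Section 10.7.4 (Adverse Events and Serious Adverse Events) begins: "If a participant has COVID-19 during the study, this should be reported as an AE or SAE and appropriate medical intervention provided". Its dosing sentence opens with "Study treatment should continue unless the". The exception that completes that sentence is a safety worry on the clinician's part, and only then does the section allow for stopping treatment, temporarily or for good. It also recommends discussing any discontinuation with the medical monitor.

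On the analysis side, SAP 6.2.3.6 states: "An interruption due to an AE is defined as a 0 mg dose administered where reason for adjustment on the dosing CRF is AE". It reports the number and percentage of patients with interruptions, using the safety analysis set as denominator. SAP 6.3.1 tabulates treatment-emergent events leading to interruption, for each drug and for any study treatment. The SAP has no separate rule for interruptions caused by COVID-19.

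**The concern.** A site with a symptomatic participant who is otherwise doing well can read two adjacent sections and reach opposite actions, each supported by the text. In 10.7.3 the symptoms alone trigger the delay. In 10.7.4 treatment goes on unless the clinician is worried. Nothing ranks the two.

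Two things are at stake. The first is participant safety, because the protocol should give one default for the same clinical situation. The second is what the safety summaries mean. COVID-19 is to be reported as an AE, so a delay can enter the AE-related interruption tables at one site and not at another for the same illness. Safety and tolerability are the only objective under Amendment 6, so these descriptive tables are part of the study's main output.

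**Working it through.** The plan states no figure for this point, so the check is a comparison of text, followed by the scale of the effect on the tables.

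**Step 1. Who is covered, and what is the default?**

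| Participant | Section 10.7.3 | Section 10.7.4 | Compatible? |
|---|---|---|---|
| Symptomatic, clinician concerned about safety | Delay at least 14 days from symptom onset | Temporary or permanent discontinuation may be required | Yes; 10.7.4 permits what 10.7.3 recommends |
| Symptomatic, clinician not concerned | Delay at least 14 days from symptom onset | Continue | **No** |
| Asymptomatic, clinician concerned | Delay guidance does not apply | Discontinuation may be required | Yes |
| Asymptomatic, clinician not concerned | Delay guidance does not apply | Continue | Yes |

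The conflict sits in one row. Confirmed and presumed infections are treated alike in 10.7.3, so that distinction adds no further conflict there.

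**Step 2. Does either section give way to the other?** Neither cites the other or states an order of precedence. Section 10.7.4 is not limited to asymptomatic infection. It provides for COVID-19 as a serious event and for medical intervention, so symptomatic illness is within its scope. Protocol Section 8 sends sites to Appendix 7 as a whole and does not choose between the two.

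**Step 3. Which analyses can change?** SAP 6.2.3.6 counts a patient when a 0 mg dose is entered with AE as the reason. SAP 6.3.1 counts events whose recorded action was interruption. Both depend on whether the site withheld drug, so both can depend on which section the site followed. They count patients and events, not days withheld.

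**Step 4. Scale.** Inputs: at most 34 participants from B1371019 and 3 from B1371012, analysed separately (SAP 2.2 and 4). One participant moving from not interrupted to interrupted changes a percentage by 100/n points:

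- B1371019, all participants: 100/34 = 2.9 points.
- B1371012: 100/3 = 33.3 points.

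These use the maximum n; a smaller safety set gives a larger shift. SAP 5.2 summarises B1371019 safety data by treatment arm. With both arms represented, each arm is smaller than 34 and the shift within an arm exceeds 2.9 points. Arm sizes are not given, so it cannot be stated more closely.

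**The case against.** The best defence is that 10.7.3 is the specific rule and 10.7.4 the general one. The first is a dosing section addressed to symptomatic cases. The second is a reporting section for all cases, and it carries a safety exception that a clinician treating a symptomatic participant might well invoke. The text leaves that reading open. It does not state it, however, and the exception depends on concern that 10.7.3 does not require.

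A second defence is that 10.7.3 only recommends. That is fair, and the point is not that sites are ordered to do two opposite things. Both sections are nevertheless phrased as what should be done, and the introduction to Appendix 7 says its measures are to be followed.

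A third defence is oversight. Section 8 asks for safety issues to be discussed with the sponsor at once, 10.7.4 recommends talking to the medical monitor about discontinuation, and 10.7.3 asks for notice at restart. These contacts make divergence less likely, but none supplies the missing default.

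Some stronger readings are tempting and are not supported:

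- **That handling will differ by site.** The documents show only that it can.
- **That the two readings differ by 14 days of dosing, or half a 28-day cycle (14/28).** The 14 days run from symptom onset, so a case recognised late may lose fewer days. Azacitidine is planned on 7 days of each 28, so a delay falling after those days may cost no azacitidine dose. The interruption table does not measure duration.
- **That the delay pushes participants toward mandatory discontinuation after 28 days.** That limit concerns glasdegib only. Section 6.6.1 also sends interruptions beyond 28 days for reasons other than treatment-related toxicity to consultation with the sponsor on resumption.

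**Conclusion.** Wrong as written: an internal contradiction, confined to symptomatic participants about whom the investigator or treating physician has no safety concern. For them the default is delay under 10.7.3 and continuation under 10.7.4, with nothing to settle which governs. The specific-over-general reading may be what the sponsor intends, but a site cannot establish that from the text.

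The consequence is possible variation in handling, which matters for safety, and possible variation in the AE-related interruption counts. Each affected participant is worth 2.9 points in B1371019 overall, more within an arm, and 33.3 points in B1371012. This assumes that the maximum numbers enter the safety set and that a delay is recorded as a 0 mg dose with AE as the reason. The total effect cannot be given, because the documents do not say how many COVID-19 cases occurred or were expected. The analyses are descriptive and no hypothesis test is affected.

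**What to change.** Reconcile Sections 10.7.3 and 10.7.4 so that a symptomatic participant, confirmed or presumed, falls under one stated default. Add a cross-reference in each section to the other. If one section is meant to govern dosing and the other only reporting, say so. Which default applies is for the sponsor's clinical team; this point takes no position on it.

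The cost is a few sentences in one protocol appendix, with the usual approval of an amendment. Data collection and the SAP tables need not change.
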